5.2.3 Baseline Values for Tumor Measurement

The baseline values for each subject will be those recorded at Visit 1. If the value at the Baseline visit is missing, then the value from the earliest available visit will be used. For tumor measurements, if the Visit 1 measurement is missing, then the measurements from the screening CT scan will be used as baseline values.

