# 9.2.1 Tumor Photography and Measurements

The primary lesion will be photographed before PRV111 treatment. This will be done to allow for a clinical assessment of response to treatment. For details refer to Study Manual for instructions.

The tumor will be measured in cm to 1 digit to the right of the decimal point using a disposable plastic ruler or caliper. Three dimensions must be recorded (Length x Width x Height).

Note: If tumor or cancerous lesion is flat, a small number (0.05 cm) will be recorded for the Height. If the tumor is a concave, a negative Height is recorded. If the height is an unmeasurable dent, it can be recorded as (-0.05 cm).

The following formula will be used to calculate tumor volume (cm^3)

$$L x W x H x \pi/6$$

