#### PCFB = % tumor volume change from the baseline

Response will be defined as CR, PR or SR. Non-Response will be defined as SD or PD (Table 4).

Table 4. Clinical Response to Treatment Based on Tumor Volume Change\*

Complete Response (CR)	Disappearance of primary lesion.		
Partial Response (PR)	PCFB: ≥30% to 69% decrease in the total tumor volume shrinkage (as determined by clinical measurement, taking as reference the baseline volume.		
Strong Response (SR)	PCFB: ≥70% to 99% decrease in the total tumor volume shrinkage (as determined by clinical measurement, taking as reference the baseline volume.		
Progressive Disease (PD)	PCFB: At least a 20% increase tumor volume as determined by clinical measurement taking as reference the baseline volume (Note: the appearance of one or more new lesions is also considered progression).		
Stable Disease (SD)	Neither sufficient shrinkage to qualify for PR nor sufficient increase to qualify for PD, taking as reference the volume determined by clinical measurement at baseline		

\* Necrosis/inflammation will not be included towards clinical tumor measurements.

9.2.3

Confidential Property of Privo Technologies, Inc. Page 39 of 59

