# 9.6.2 Baseline, Treatment (Visit 1)

Occurs within 28 days following Screening visit (Visit 0). Predose Assessments (Baseline):

- Verify inclusion/exclusion criteria
- Perform and record result of physical examination and VS

- Perform and record visual oral cavity examination and neck lymph node examination
- Perform and document baseline clinical tumor measurement
- Collect clinical labs: blood draw for CBC, chemistry panel (creatinine for determining creatinine clearance, BUN, LFT, electrolytes [potassium, magnesium, calcium, and sodium], hCG [urine] for females of childbearing potential), and perform urinalysis.
- Administer oral anti-emetics (ondansetron or promethazine, the dose to be determined at the discretion of the PI) before the start of PRV111 treatment
- Photograph the tumor
- Draw blood for PK (-15 to 0 minutes predose)
- Administer PE (refer to Pharmacy Manual for administration instructions)
  - document time of application
  - ask for taste of PE solution
- Administer PRV111 patch(es) and document time of each application and removal. Ask for taste of patch.

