#### 9.6.6 Post-Treatment/Pre-Op Visit (Visit 5)

- Occurs a minimum of 72 hours after the last visit and prior to surgery. Perform and document physical examination and VS
- Perform and document visual oral examination and neck lymph node examination
- •
- Perform and document clinical tumor measurement and Tumor volume CFB criteria
- ECG
- Collect clinical labs: blood draw for CBC, chemistry panel (creatinine, BUN, LFT, electrolytes [potassium, magnesium, calcium, and sodium], and perform urinalysis
- Photograph the tumor
- Record AEs as reported by subject or observed by Investigator
- Review any concomitant therapy

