3.1 PRIMARY: Tumor Photography and Measurements

The primary lesion will be photographed before PRV111 treatment. This will be done to allow for a clinical assessment of response to treatment. For details refer to Study Manual for instructions.

The tumor will be measured in cm to 1 digit to the right of the decimal point using a disposable plastic ruler or caliper. Three dimensions must be recorded (Length x Width x Height).

Note: If tumor or cancerous lesion is flat, a small number (0.05 cm) will be recorded for the Height. If the tumor is a concave, a negative Height is recorded. If the height is an unmeasurable dent, it can be recorded as (-0.05 cm). The volume calculations use the heights absolute value. The following formula will be used to calculate tumor volume (cm³)

$$L \times W \times H \times \pi/6$$

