6.2 Handling of Missing Data

All missing data will be queried. Missing efficacy data which are not retrievable through queries will be imputed. Missing safety data will not be imputed. If the value of a vital sign assessment, ECG variable, laboratory value, or clinical tumor measurement is missing at Baseline, then CFB will be defined as the change from the value recorded at the next earliest available data point.

Non-Responder Imputation (NRI)

No missing values imputation will be applied.

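### SAP 5.2.3 replaces a missing Visit 1 tumor measurement with screening CT dimensions, so the primary percent change mixes CT with ruler or caliper and can be misclassified in either direction

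*SAP*

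**What the plan says.** **Planned measurement.** Protocol 9.2.1 and SAP 3.1 have the tumor measured in three dimensions "using a disposable plastic ruler or caliper", to 0.1 cm. Volume is L × W × H × π/6, and the SAP uses the absolute value of height. A flat lesion is given a height of 0.05 cm.

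**Visits.** Protocol 9.6.2 (Visit 1) lists "Perform and document baseline clinical tumor measurement". Protocol 9.6.6 (Visit 5) lists "Perform and document clinical tumor measurement and Tumor volume CFB criteria". SAP 3.1.2 bases the final efficacy determination on the change from Visit 1 to Visit 5.

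**Response table.** In Protocol 9.2.2, Table 4 (repeated in SAP 3.1.1), the partial response, strong response and progression rows all refer to clinical measurement. The stable disease row is explicit about the baseline: "taking as reference the volume determined by clinical measurement at baseline".

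**Missing baseline.** The SAP gives three rules:
- SAP 5.2.3, general: "If the value at the Baseline visit is missing, then the value from the earliest available visit will be used".
- SAP 5.2.3, tumor measurements: "if the Visit 1 measurement is missing, then the measurements from the screening CT scan will be used as baseline values".
- SAP 6.2, which names the clinical tumor measurement among its variables: "then CFB will be defined as the change from the value recorded at the next earliest available data point".

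The readable protocol has no CT fallback, and SAP section 7 plans no changes from the protocol.

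**The concern.** When the fallback is used, the denominator of the primary percent change comes from CT and the numerator from a ruler or caliper. That departs from the endpoint's own definition. Any disagreement between the instruments is then counted as tumor change, as is any real change between the scan and Visit 1. Protocol 9.6.1 allows screening tests up to 28 days before Visit 1.

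The readable text has no conversion, no agreement check and no sensitivity analysis for such a subject. The subject also stays in the primary analysis, because the Evaluable Population (SAP 5.2.2) requires eligibility and at least 75% of the dose, not a Visit 1 tumor measurement.

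Volume is a product of three dimensions, so modest linear differences multiply, and the success rule rests on at most 11 subjects. A misclassified Stage 1 subject would also enter the Stage 1 dose rule, which turns on 2 or fewer against 3 or more responses.

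**Working it through.** **Inputs from the documents.** Response: volume decrease of at least 30%. Progression: increase of at least 20% (Table 4). Success: at least 7 responses in 11 (SAP 3.1.2). Design: p0 = 0.30, p1 = 0.85, n1 = 5, r1 = 2, N = 11, R = 6, type I error 0.018, power 96.44% (Protocol 10.2). The documents give no figure for CT-versus-ruler disagreement, so every difference below is an assumption.

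**Step 1: reproduce the plan's figures.** P(success) = Σ over x = 3 to 5 of b(x; 5, p) × P(Bin(6, p) ≥ 7 − x), where b is the binomial probability.
At p = 0.30: 0.1323 × 0.07047 + 0.02835 × 0.25569 + 0.00243 × 0.57983 = 0.0180.
At p = 0.85 the same sum is 0.9644. Both match the protocol.

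**Step 2: percent change with no true tumor change.** If CT exceeds the ruler by a fraction d in each dimension, PCFB = 100 × [1/(1 + d)³ − 1].

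| Assumed CT difference per dimension | PCFB | Category |
|---|---|---|
| +5% | -13.6% | SD |
| +10% | -24.9% | SD |
| about +12.6% | about -30% | PR threshold |
| +15% | -34.2% | PR |
| +20% | -42.1% | PR |
| -5% | +16.6% | SD |
| -6% | +20.4% | PD |
| -10% | +37.2% | PD |

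The PR threshold solves (1 + d)³ = 1/0.70, so d is about 0.126. The PD threshold solves 1/(1 + d)³ = 1.20, so d is about -0.06.

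If only height differs, PCFB = 100 × (H_ruler/H_CT − 1). An assumed 0.2 cm by ruler against 0.3 cm by CT gives -33.3% (PR). The flat-lesion value of 0.05 cm against 0.3 cm by CT gives -83.3% (SR).

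**Step 3: effect of one certain false responder.** One subject is 1/11 = 9 percentage points of response rate. Set that subject to response and let the other ten respond at 0.30.
- Stage 1 subject: Σ over x = 2 to 4 of b(x; 4, 0.3) × P(Bin(6, 0.3) ≥ 6 − x) = 0.2646 × 0.07047 + 0.0756 × 0.25569 + 0.0081 × 0.57983 = 0.043.
- Stage 2 subject: Σ over x = 3 to 5 of b(x; 5, 0.3) × P(Bin(5, 0.3) ≥ 6 − x) = 0.1323 × 0.16308 + 0.02835 × 0.47178 + 0.00243 × 0.83193 = 0.037.

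These apply where the dose is kept and both stages are pooled.

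**Step 4: effect of counting one such subject as a non-responder.**
- Stage 1 subject: Σ over x = 3 to 4 of b(x; 4, p) × P(Bin(6, p) ≥ 7 − x) = 0.0074 at p = 0.30 and 0.870 at p = 0.85.
- Stage 2 subject: Σ over x = 3 to 5 of b(x; 5, p) × P(Bin(5, p) ≥ 7 − x) = 0.0098 at p = 0.30 and 0.939 at p = 0.85.

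**The case against.** **The trigger may never occur.** Visit 1 measurement is a scheduled pre-dose procedure and SAP 6.2 queries all missing data. This stands as a limit on likelihood. It does not justify a rule that breaks the endpoint definition when it is used.

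**A bias towards response is not shown.** A reader might infer that CT captures tissue below the mucosal surface while a ruler sees only what projects, so that a CT baseline would usually be larger and the error would favor response. The documents do not support that: no readable passage says how CT dimensions are taken or compares them with a ruler. If the tumor grew between the scan and Visit 1, the CT baseline would be too small and would hide a response. Only misclassification in either direction can be claimed.

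**Redaction.** Some schedule rows and protocol sections are blacked out. One masked SAP schedule row is marked at Screening and Visit 5, and a SAP schedule footnote asks for the same test at both timepoints. A matched second scan therefore cannot be excluded. But that footnote has no legible link to the tumor measurement row, and the readable plan makes the Visit 5 efficacy value clinical.

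**Overlap with the conflict between SAP 5.2.3 and 6.2.** The conflict is real and leaves the baseline undefined. Resolving it in favor of the CT sentence would keep the present problem. Deleting only that sentence would leave two rules that could take a post-dose visit as baseline.

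**Conclusion.** The point holds as a contradiction between the SAP's baseline fallback and the endpoint definition. The fallback can turn a difference between instruments, or a change before Visit 1, into a response or a progression. Under a uniform per-dimension difference and an unchanged tumor, a CT excess of about 12.6% or a shortfall of about 6% is enough to cross a category boundary.

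The type I error figures in Step 3 are a worst case: they assume that one false response is certain and that the other ten subjects respond at 0.30. They do not estimate what will happen, since neither the frequency of missing Visit 1 values nor the size or direction of the instrument difference is documented. The point deserves correction because a single subject can decide a result at the boundary of 6 or 7 responses, and the correction is short.

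**What to change.** 1. Delete the CT substitution from SAP 5.2.3, and state there that the earliest-available-visit rule does not apply to tumor volume.
2. Remove the clinical tumor measurement from the missing-baseline fallback in SAP 6.2, so that no post-dose visit can become the baseline.
3. State that the primary percent change is calculated only from clinical measurements at Visit 1 and Visit 5.
4. Count an evaluable subject without a clinical Visit 1 measurement as a non-responder. Amend the closing sentence of SAP 6.2, which rules out imputation, to match.
5. Show any CT-based value in a listing or sensitivity analysis only.

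**Cost.** The edits are a few sentences in two SAP sections. A subject with a missed baseline reading can no longer count as a response. With one such subject, power at 0.85 falls from 96.4% to 87.0% (Stage 1) or 93.9% (Stage 2), while type I error stays below 0.018. Excluding the subject is an alternative; non-responder counting is preferred here because it is conservative and keeps the planned denominator.

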5.2.4 Change from Baseline (CFB) and Percent Change from Baseline (PCFB)

CFB will be calculated at each post-baseline visit for all evaluable subjects as:

$$\text{CFB} = \text{Post-Baseline value} - \text{Baseline value.}$$

CFB will be reported to the same number of decimal places as the variable.

PCFB will be calculated at each post-baseline visit for all evaluable subjects as:

$$\begin{aligned} \text{PCFB} &= 100 * \text{CFB} / \text{Baseline value} \\ &= 100 * (\text{Post-Baseline value} - \text{Baseline value}) / \text{Baseline value.} \end{aligned}$$

PCFB will be reported to same number of decimal places as the variable.

5.2.5 Descriptive Summary Statistics

The following standards will be applied for each analysis unless otherwise specified. Simple summary statistics for continuous data are defined as: n (number of non-missing observations), mean, standard deviation, maximum, median, minimum. The number and percentage of subjects will be used to summarize categorical data. All data will be listed and sorted by investigator number, variable, subject number, and visit, if appropriate.

5.3 Safety Analyses

The Safety Population will be used for all summaries of safety data.

will be used in the calculation of the incidence of individual TEAE by relationship.

5.3.1 Safety Population

All subjects who have at least 1 PRV111 patch applied will be included in the Safety Population.

5.3.2 Concomitant Medication and Therapy

A listing of concomitant medications and therapy will be provided for the Safety Population.

5.3.3 Medical History, Medication History and Baseline Disease Characteristics

Medical history and baseline disease characteristics will be listed for the Safety Population.

ECOG PS (Appendix 2) will be included.

5.3.4 Subject Accountability, Demographics, and Baseline Characteristics

Subject completion status, dose modification, and study terminations will be summarized for each of the study stages and for the study overall. Subjects with major protocol violations will be listed. Demographics will be summarized along with baseline characteristics such as medical history, and baseline physical examination, weight, VS, ECOG PS, and concomitant therapy.

6 Data Handling

6.1 Pooling of Centers

This is a multi-center study. The data from all sites will be pooled for all analyses.

6.2 Handling of Missing Data

All missing data will be queried. Missing efficacy data which are not retrievable through queries will be imputed. Missing safety data will not be imputed. If the value of a vital sign assessment, ECG variable, laboratory value, or clinical tumor measurement is missing at Baseline, then CFB will be defined as the change from the value recorded at the next earliest available data point.

Non-Responder Imputation (NRI)

No missing values imputation will be applied.

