#### 9.3.5 Electrocardiograms

Electrocardiograms (ECGs) will be evaluated for clinically relevant changes from Baseline.

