## 9.6.1 Screening (Visit 0)

- Visit and all historical exams/tests must occur within 28 days prior to initial treatment (Visit 1). Confirmed SCC
- Obtain and document consent from potential subject on Informed Consent Form (ICF)
- Review inclusion/exclusion criteria to determine eligibility
- Review demographics, medical and medications history to determine eligibility based on inclusion/exclusion criteria
- Obtain or perform a general physical examination (must be within 14 days of first dose) and check VS
- Perform a systematic and thorough visual and manual examination of the oral cavity mouth and cervical and local lymph nodes examination
- Obtain historical or perform an ECG
- •
- Perform clinical labs: blood draw for complete blood count (CBC), chemistry panel (creatinine for determining creatinine clearance, blood urea nitrogen (BUN), liver function test (LFT), electrolytes [potassium, magnesium, calcium, and sodium], hCG [serum]) for females of childbearing potential and perform urinalysis.
- AE documentation begins after subject signs the ICF
- Schedule study visits
- Obtain historical or test tissue for HPV

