## **Postdose Assessments:**

- Draw blood for PK 30±5 minutes, 60±5 minutes and 120±5 minutes following application of the last patch at that treatment visit.
- VS shall be monitored at 30±5 minutes, 60±5 minutes and 120±5 minutes following application of the last patch applied.
- Collect all used patches (include the ones that detached prematurely), record the time of the detachment of each patch, store the patches in the plastic bags supplied by the Sponsor (refer to Laboratory Manual for instructions).
- Record AEs as reported by subject or observed by Investigator
- Review any concomitant therapy
- Schedule study visits

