4.4 Safety Laboratory Assessments

Clinical laboratories to be assessed will be as in [Table 3](#).

[figure not shown]
Table 3. Clinical Laboratories

COMPLETE BLOOD COUNT	CHEMISTRY PANEL	

 • hematocrit • hemoglobin • platelet count • red blood cell count • white blood cell count and differential (absolute and percentage); neutrophils, lymphocytes, monocytes, eosinophils, basophils, and reticulocyte count 	
 • alanine aminotransferase • albumin • alkaline phosphatase • aspartate aminotransferase • bilirubin (direct and total) • blood urea nitrogen • calcium • CO₂ 	
 • chloride • creatinine^a • gamma glutamyl transferase • glucose • magnesium • potassium • sodium • total protein
URINALYSIS		

 • urinalysis dipstick with reflex microscopic examination for abnormalities 		

^a Creatinine Clearance will be used to assess renal function using Cockcroft-Gault Equation

4.4.1 Laboratory Tests Analysis:

Laboratory values such as routine blood chemistry, hematology, and urinalysis will be measured for each subject. Summary statistics will be provided by visit for blood chemistry and hematology and the corresponding CFBs. The calculation for CFB is described in Section 9.5. If the value at Baseline is missing, then CFB will be defined as the change from the value recorded at Screening. Urinalysis results and serum and urine pregnancy test results will be included in the listings of laboratory parameters but not in the summary tables. Laboratory ranges displayed and used for normal values will be per site. If a laboratory is missing ranges, the next most-similar lab will be used. For example, if Site 001 is missing a normal range, another lab from the same site will be used as reference (i.e. Baylor HHS is missing red blood cells, the value from Baylor Austin will be used). Data will be displayed per lab and per patient.

[figure not shown]

4.5 *Electrocardiograms*

Electrocardiograms (ECGs) will be evaluated for clinically relevant changes from Baseline.

4.5.1 ECG Parameters Analysis:

ECG parameters will be reported as normal or abnormal per subject and per visit.

4.6 *Adverse Event Definitions/Reporting Requirements*

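### SAP 6.2 does not require a replacement for a missing safety baseline to be pre-dose, two other SAP rules are worded differently, and no ECG baseline is named

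*SAP*

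**What the plan says.** SAP 5.2.3 fixes baseline at Visit 1, and Protocol 9.6.2 labels the Visit 1 pre-dose assessments as baseline. Three SAP sections then say what to do when that value is absent.

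- **SAP 6.2** covers vital signs, ECG variables, laboratory values and clinical tumor measurements: if the value "is missing at Baseline, then CFB will be defined as the change from the value recorded at the next earliest available data point". The same section says "Missing safety data will not be imputed".
- **SAP 4.4.1** covers laboratory values: "If the value at Baseline is missing, then CFB will be defined as the change from the value recorded at Screening". It sends the reader to a Section 9.5 for the calculation, but the SAP ends at Section 8.
- **SAP 5.2.3** is headed as a rule for tumor measurement but contains a general sentence: "If the value at the Baseline visit is missing, then the value from the earliest available visit will be used".

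SAP 4.1.1 plans numeric change from baseline for vital signs, summarized by visit. SAP 4.4.1 plans the same for chemistry and hematology. For ECG, Protocol 9.3.5 says "Electrocardiograms (ECGs) will be evaluated for clinically relevant changes from Baseline" and SAP 4.5 repeats this, while SAP 4.5.1 reports only normal or abnormal for each subject and visit. The Screening list in Protocol 9.6.1 includes "Obtain historical or perform an ECG", and the schedule of events has the next ECG at Visit 5.

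**The concern.** A baseline for a safety summary should come from before exposure. SAP 6.2 sets neither a direction in time nor a pre-dose limit, so a value recorded after PRV111 can become the reference. Any effect already present when that value was taken is then subtracted out of every later change.

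The three rules can also give different answers for the same subject. Two programmers could each follow the SAP and produce different laboratory tables.

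This matters because Protocol 6.2 describes the trial as first-in-human and Protocol 4.3 names renal toxicity among the known effects of systemic cisplatin. The groups are also small. Stage 1 seeks 5 evaluable subjects from up to 10 enrolled, so with 5 to 10 treated subjects, one subject carries 1/5 = 20% to 1/10 = 10% of a mean.

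**Working it through.** The plan gives no figure to reproduce here. The check applies each rule to the schedule of events (Protocol Table 1, SAP 2.11, Protocol 9.6.1 to 9.6.7) for a subject with no Visit 1 pre-dose value.

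| Variable | When scheduled | SAP 6.2 read forward | SAP 6.2 read as earliest on record, or SAP 5.2.3 | SAP 4.4.1 |
|---|---|---|---|---|
| Vital signs | Screening; pre-dose at Visits 1–4; 30, 60 and 120 min after last patch at Visits 1 and 4; 30 min at Visits 2 and 3; Visit 5 | Visit 1, 30 min after last patch (or Visit 2 pre-dose if only pre-dose values count) | Screening | Not covered |
| Laboratory | Screening; Visits 1 and 3 pre-dose; Visit 5; surgery | Visit 3 | Screening | Screening |
| ECG | Screening; Visit 5 | Visit 5 | Screening | Not covered |

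**Vital signs.** Protocol 9.6.2 requires post-dose readings at Visit 1: "VS shall be monitored at 30±5 minutes, 60±5 minutes and 120±5 minutes following application of the last patch applied". The first of these, or the Visit 2 pre-dose value, follows at least one treatment. SAP 6.2 is the only missing-baseline rule that names vital signs, and a numeric change is tabulated from it.

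**Laboratory values.** Let S, L3 and L5 be the Screening, Visit 3 and Visit 5 results. Visit 3 blood is drawn before that visit's dose, after two of the four treatment visits.

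- SAP 4.4.1: change at Visit 3 = L3 − S; change at Visit 5 = L5 − S.
- SAP 6.2 read forward: change at Visit 3 = L3 − L3 = 0; change at Visit 5 = L5 − L3 = (L5 − S) − (L3 − S).

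The two rules differ at both visits by L3 − S, the whole change seen after the first two treatment visits. The documents do not say how large that is.

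**ECG.** No subject has a planned Visit 1 ECG, so a baseline set at Visit 1 has no ECG value. A pre-treatment one exists: the schedule's footnote on historical data allows an earlier ECG only within 28 days before first treatment, so the Screening ECG is pre-dose.

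**Which way does SAP 6.2 read?** The forward reading is a natural one. The sentence also covers clinical tumor measurement, which the schedule starts at Visit 1, so for that variable the next scheduled clinical measurement after a missing Visit 1 value is Visit 2. And where the authors wanted Screening, in SAP 4.4.1, they wrote it.

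**The case against.** **The wording sets no direction.** SAP 6.2 can be read as pointing to the earliest value on record, which is Screening for all three safety variables; the general sentence in SAP 5.2.3 leads there too. This stands as a possible reading. It does not settle the matter, because the heading of SAP 5.2.3 limits it to tumor measurement and SAP 6.2 does not exclude post-application values.

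**Laboratory values have their own rule.** A specific rule would ordinarily prevail over a general one, so SAP 4.4.1 should govern in practice. That is fair, and it makes vital signs the main exposure. The contradiction remains, since SAP 6.2 names laboratory values and no order of precedence is given.

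**Safety data are not to be imputed.** This does not help: the sentence that follows in SAP 6.2 supplies a substitute reference for named safety variables.

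**Signals would still be seen.** Observed vital signs are summarized and listed beside their changes, clinically significant laboratory abnormalities are summarized separately, and dose-limiting toxicity is defined by grade and clinical criteria (Protocol 8.2, SAP 2.10). All of this stands and limits the consequence.

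**Stronger inferences that do not hold.**
- A reader might infer that the Visit 5 ECG becomes its own reference for every subject. That requires the forward reading and also requires an ECG never planned at Visit 1 to count as missing. SAP 4.5.1 in any case plans no subtraction.
- A reader might infer that a treated reference always biases towards no change. It forces zero only at the reference point; if a post-patch reading is transiently high, later values appear as decreases.
- A reader might put the Visit 5 laboratory change at half the true effect. That assumes equal effect per treatment visit, which the documents do not give.

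**Conclusion.** The point holds as a defect in the analysis rules for descriptive safety summaries. SAP 6.2 permits a post-PRV111 reference. This bites mainly on vital signs, which no other rule names and for which a numeric change is tabulated. For laboratory values SAP 6.2, read forward, contradicts SAP 4.4.1, and the results differ by the full change from Screening to Visit 3. For ECG the baseline visit is not named, but the effect on output is small because only normal or abnormal is reported.

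For vital signs and laboratory values the size depends on how many subjects lack a Visit 1 pre-dose value after querying, which the documents do not state; if none do, those tables are unaffected. The conclusion that a treated value is used rests on the forward reading. The inconsistency between sections and the missing ECG baseline do not. Dose decisions are not affected.

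**What to change.** Put one rule for safety variables in SAP 6.2 and make SAP 4.4.1 and 5.2.3 agree with it: *Baseline is the last non-missing value recorded before the first permeation enhancer or patch application (Visit 1 pre-dose, otherwise Screening); a post-application value is never used as baseline.* In SAP 4.5, name Screening as the ECG baseline, and in 4.5.1 add a table of the normal/abnormal shift from Screening to Visit 5. Correct the reference to Section 9.5 in SAP 4.4.1 at the same time.

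The cost is SAP wording and one small ECG table. No new data are needed, since vital signs, laboratory tests and ECG are all scheduled at Screening. The downside is that a subject with no pre-dose value at all drops out of that change-from-baseline summary; the observed values can still be listed.
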